1. PURPOSE AND OBJECTIVES

This is a prospective study to evaluate the PICOSURE Laser System for the treatment of unwanted tattoos.

Objectives:

1. Establish Treatment parameters
2. Compare to Revlite Laser System
3. To assess safety through recording of side effects during course of study.

2. BACKGROUND

Lasers are accepted devices for the removal of unwanted tattoos. Currently, Q switched Alexandrite and Nd:YAG lasers emitting wavelengths of 1064nm, 755nm and 532nm, are routinely used in the removal of unwanted tattoos. The lasers' Q-switched mode of operation allows the delivery of short (nanosecond) pulses that can disrupt or shatter the tattoo ink or pigment which is subsequently cleared by the body's own cells, the phagocytes or macrophages.

Tattoo removal often requires a series of treatments performed approximately every 6 weeks. Tattoos may be removed in as few as 2-4 treatments, but others may require six to ten, or even as many as twenty treatments to achieve clearance. Unfortunately, not all tattoos can be removed completely.

3. DEVICE DESCRIPTION

The RevLite Q-Switched Nd:YAG is cleared under FDA K083899 for Tattoo Removal. The PICOSURE laser has been cleared by the FDA under 510 (k) K121346 for the removal of tattoos and benign pigmented lesions. It is believed that these shorter pulses may be more efficient in disrupting pigment and possibly resulting in better treatment outcomes.

The sponsor deems this device a non significant risk. The system was tested to ensure compliance with federal laser performance standards, 21CFR Part 1040.

See section 11 for full specifications.

4. SUBJECT POPULATION AND SELECTION CRITERIA

The study subject population will consist of up to 100 subjects. Up to 10 subjects will be receiving split tattoo treatments with the Revlite and/or the Pico Laser. The subjects will meet the selection criteria described as follows:

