5.1 Subject Assignment

All potential subjects will undergo a pre-screening interview where their medical history will be reviewed and inclusion/exclusion criteria verified. Subjects meeting the criteria for enrollment in the study will sign the informed consent form and be assigned a subject identification number. Subject identification numbers will be generated chronologically and assigned only to subjects who have met all inclusion/exclusion criteria and signed the informed consent form. Subjects will be de-identified through their subject identification number, which will be stored in a secure location.

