5.3.3 Technique

- The appropriate parameters including the number of pulses will be determined by the physician.
- The laser hand piece distance gauge tip will be in contact with the skin.

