5.7 Evaluation Methods

5.7.1 Tattoo Clearance

A photographic Scale will be used to evaluate outcomes. Blinded evaluators will grade the tattoo clearance of photographs taken of the subjects at baseline and post treatment. The results will be compared to determine improvement.

5.7.2 Investigator and Subject Questionnaires:

Questionnaires will be used to assess Investigator and Subject satisfaction at the 2 month follow up visit with their cosmetic results when compared to baseline photos using a six point scale ranging from “extremely satisfied” to “extremely dissatisfied”.

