## PicoRev Sample Size Rationale

The primary objectives of this study include establishing treatment parameters, assessing safety of the treatment, and comparison of the PicoSure laser to the RevLite laser. Due to the wide variety of treatment parameters to be assessed it was decided to outline up to 10 different treatment subgroups to help further identify subjects based on subject demographics, tattoo characteristics, and additional parameters that may need to be established but are not currently identified. If we assume we a treatment effect of a score of 2 on the tattoo clearance grading (0-3) which corresponds to 50% identifies a treatment effect, with a set power of 95% and a two sided significance level of 0.05, it results in a required study population of 6 subjects for each treatment subgroup. To account for subjects withdrawing or potential lost-to-follow ups due to the extended timeframe of up to 10 treatments every six weeks, it was decided to enroll up to 10 subjects in each group. With a potential of 10 total groups, it is determined that up to 100 subjects may be enrolled in the study.

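### The PicoSure–RevLite comparison has no rule for assigning the parts of a split tattoo to a laser, so laser effect and choice of part cannot be separated

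*Protocol*

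**What the plan says.** Protocol section 1 gives as its second objective "Compare to Revlite Laser System", without ranking it. The SAP's sample size rationale puts "comparison of the PicoSure laser to the RevLite laser" among the primary objectives.

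How the comparison is made rests on one sentence in Protocol section 4: "Up to 10 subjects will be receiving split tattoo treatments with the Revlite and/or the Pico Laser".

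The places where an allocation rule could sit do not contain one:

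- Section 5.1 (Subject Assignment) deals with eligibility, consent and numbering: "Subject identification numbers will be generated chronologically and assigned only to subjects who have met all inclusion/exclusion criteria".
- Sections 5.2 and 5.3 do not say how a tattoo is divided. Section 5.3.3 leaves settings to judgement: "The appropriate parameters including the number of pulses will be determined by the physician".
- Section 5.7.1 supplies the one control on bias: "Blinded evaluators will grade the tattoo clearance of photographs taken of the subjects at baseline and post treatment".
- Section 15 names the outcomes to be analysed but no between-laser or within-subject method.
- The SAP gives a sample size rationale only.

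**The concern.** A split-tattoo design holds the person constant. It does not hold the part constant. If someone picks which part gets which laser, laser and part are confounded, and no analysis of up to 10 pairs can separate them afterwards.

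The protocol gives some reason to think the choice may not be neutral: section 3 records the belief that shorter pulses may lead to better outcomes. Grading against baseline allows for how a part looked at the start, not for how readily it clears. Blinded grading acts after the part has been chosen and treated.

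A smaller point is the wording *and/or* in section 4. The natural reading is one laser per part, but it also permits a split tattoo treated with one laser only. Such a tattoo contributes nothing to the laser comparison.

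**Working it through.** **The plan's own figure.** The SAP requires 6 subjects per subgroup for an effect of 2 on the 0–3 clearance grade, "with a set power of 95% and a two sided significance level of 0.05". It gives neither an SD nor a test, so the figure cannot be confirmed. A one-sample or paired t-test gives 6 if the SD is assumed to be 1.0 (5 at 0.90, 7 at 1.1). A two-sample t-test gives 6 at an SD of about 0.77–0.86. The figure is not stated to apply to a between-laser difference. Below, 6 and 10 serve only as plausible numbers of complete pairs: the SAP's required number per subgroup and the protocol's ceiling.

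**Inputs**
- Pairs: n = 10 (Protocol section 4) or n = 6 (SAP).
- Two-sided significance level 0.05 (SAP).
- Assumed, not in the documents: a paired t-test on roughly normal differences, no true laser effect, and a shift b in the mean paired difference caused by part choice, in units of the SD of that difference. Values tried: 0.25, 0.5 and 1.0.

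**Effect of the missing rule.** Under shift b the paired t statistic is noncentral t with n − 1 degrees of freedom and noncentrality b√n. The false-positive rate is P(|T| > t₀.₉₇₅,ₙ₋₁).

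| b (SD) | b√10 | 10 pairs, chosen | 10 pairs, randomised | b√6 | 6 pairs, chosen | 6 pairs, randomised |
|---|---|---|---|---|---|---|
| 0.25 | 0.79 | 10.9% | 4.9% | 0.61 | 8.0% | 5.0% |
| 0.5 | 1.58 | 29.3% | 5.0% | 1.22 | 17.1% | 5.1% |
| 1.0 | 3.16 | 80.3% | 5.2% | 2.45 | 50.7% | 5.4% |

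The randomised columns are simulated, 200,000 runs each. The parts differ by the same amount, but the sign of the difference is set by simple randomisation. Simulation of the chosen columns agrees with the formula (10.9/29.5/80.1% for 10 pairs, 7.9/17.0/50.8% for 6).

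**Precision, which random assignment does not change.** The 95% CI half-width is t₀.₉₇₅,ₙ₋₁/√n, in SDs of the paired difference:
- 10 pairs: 2.262/√10 = 0.715. Detectable difference 1.29 SD at 95% power, 1.00 SD at 80%.
- 6 pairs: 2.571/√6 = 1.049. Detectable difference 1.87 SD at 95% power, 1.43 SD at 80%.

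**The case against.** **The operator's choice is inferred from silence.** True. No sentence says that the operator chooses, and the case report form and operator manuals were not available for review. The omission itself is certain, nothing in either document prevents a choice, and the protocol does not point to an appendix for allocation.

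**The SAP's interest in tattoo characteristics concerns differences between subjects.** This largely stands. The SAP wants subgroups to "identify subjects based on subject demographics, tattoo characteristics", which is not evidence that parts of one tattoo clear differently. It shows only that the sponsor thinks such characteristics may matter. How much parts of one tattoo differ is unknown.

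**The error rates come from a test the plan does not specify.** This also stands. The shifts are assumed, and the outcome is a four-level grade rather than a normal variable. At the smallest shift the rate is only 8–11%. The table shows how the bias works and does not estimate its size.

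**The precision figures do not measure this defect.** Agreed. They are given so that the report does not claim more than up to 10 pairs can show.

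**Randomising the halves is a partial cure.** Correct. The physician still sets the parameters on each half and is not said to be blinded. Section 5.7.1 also does not say what the graders are blinded to.

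**The subset is small, and only the SAP ranks this objective as primary.** It is up to 10 of up to 100 subjects. That limits the damage to one objective. It does not excuse the gap, because the choice cannot be undone once treatment has started.

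**Conclusion.** The concern holds. The plan makes the laser comparison an objective, primary in the SAP, and confines its description to up to 10 split tattoos with no random, alternating or fixed assignment of part to laser. Carried out as written, it cannot attribute a difference to the laser.

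The size of any bias cannot be derived from the documents. Under the assumed shifts of 0.25 to 1.0 SD, the nominal 5% error rate becomes 11–80% with 10 pairs and 8–51% with 6. Random assignment keeps it at about 5%. These rates assume a paired t-test, normal differences and equal lasers.

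The conclusion that laser and part are confounded needs none of those assumptions. The plan should be changed before the split tattoos are treated. The objectives on treatment parameters and safety are not affected by this point.

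**What to change.** 1. In Protocol section 4, drop *and/or* for the comparison group and state that each such tattoo has one half treated with each laser. Keep any single-laser splits out of the laser comparison.
2. In section 5.1, say how the halves are defined (for example left/right or upper/lower) and have them marked on the baseline photograph. Only then open a computer-generated random list that assigns laser to half.
3. In section 15, specify analysis of the within-subject difference in blinded clearance grade, with a 95% CI.
4. Record grade, satisfaction and events for each half, if the case report form does not already do so.
5. Keep the ceiling of 10 and state the precision it gives: a half-width of about 0.72 SD with 10 complete pairs, 1.05 SD with 6.

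The cost is a short amendment, which section 19 requires the IRB to approve in writing, a one-page list, and possibly an extra line per half on the form and questionnaire. No subjects or visits are added.

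The downsides are real but modest. The operator loses the choice of half. Tattoos for which the physician would not accept either laser on either half cannot enter the comparison. Single-laser splits use up places under the ceiling. Settings stay at the physician's discretion, so the report should describe the contrast as one between lasers used with physician-chosen parameters.

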5. STUDY DESIGN

Subjects will receive up to 10 laser treatments on their unwanted tattoo. The study subjects will return to the investigator site for follow-up evaluations. See section 5.4 for schedule and visit details.

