15. DATA ANALYSIS

In order to meet the objectives of our clinical study we will analyze tattoo clearance scores, PI and Subject satisfaction, and events.

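### The PicoSure–RevLite comparison is a primary objective, but the only rule that gives anyone RevLite does not require both lasers on a split tattoo, sets no minimum number and does not say how tattoo parts are assigned

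*Protocol*

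**What the plan says.** The SAP (PicoRev Sample Size Rationale) names three primary objectives, one of which is "comparison of the PicoSure laser to the RevLite laser". Protocol Section 1 lists the same comparison as objective 2 of 3.

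Protocol Section 4 holds the only rule that places subjects on RevLite: "Up to 10 subjects will be receiving split tattoo treatments with the Revlite and/or the Pico Laser". Elsewhere RevLite appears only in the objectives, the device clearance and specifications, the risk text and the list of manuals.

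The sections where an allocation rule would be expected do not give one:

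- Section 5 (Study Design) names no laser: "Subjects will receive up to 10 laser treatments on their unwanted tattoo".
- Section 5.1 (Subject Assignment) covers identification numbers only: "Subject identification numbers will be generated chronologically and assigned only to subjects who have met all inclusion/exclusion criteria".
- Section 5.3.3 (Technique) leaves the settings to the physician: "The appropriate parameters including the number of pulses will be determined by the physician".
- Sections 5.3.2 and 5.4 give the treatment interval and visits without naming a laser.

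The SAP's only calculation is per subgroup: "it results in a required study population of 6 subjects for each treatment subgroup". It then adds an allowance for losses: "it was decided to enroll up to 10 subjects in each group". The subgroups are based on demographics, tattoo characteristics and parameters still to be identified. Laser is not named as a basis.

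Section 15 gives the whole analysis plan: "In order to meet the objectives of our clinical study we will analyze tattoo clearance scores, PI and Subject satisfaction, and events". It states no between-laser contrast.

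**The concern.** A split-tattoo comparison gets its strength from pairing. Each subject contributes a PicoSure part and a RevLite part of the same tattoo, so ink, skin type and site are largely shared. That works only if both lasers are used on the tattoo, enough subjects are treated this way, and the choice of part for each laser does not depend on how the part looks.

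The protocol secures none of the three. A split treated with PicoSure alone at two settings would serve objective 1 (treatment parameters) and would satisfy the Section 4 sentence, yet it adds nothing to the laser comparison. If the operator picks the parts, one laser may get the denser, more colourful or more awkward area. The blinded photographic grading in Section 5.7.1 does not protect against that, because the imbalance is already in the tattoo.

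The number of pairs and the choice of parts are both fixed when treatment is given. An analyst cannot supply them afterwards.

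**Working it through.** **1. The plan's own figure.** Stated inputs: effect = a score of 2 on a 0–3 grade, power 95%, two-sided 0.05, result 6 per subgroup. The SAP gives no SD, test or comparator, so 6 cannot be derived from these inputs alone. Solving for the SD that returns 6:

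- One-sample or paired normal approximation, n = ((1.960 + 1.645) × SD / 2)², rounded up: SD about 1.24 to 1.36. For example, SD 1.25 gives (3.605 × 0.625)² = 5.08, so 6.
- One-sample or paired t-test: SD about 0.91 to 1.07.
- Two-sample t-test with 6 per arm: SD about 0.76 to 0.86.

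So 6 is plausible for a range of assumptions, but nothing links it to a difference between lasers.

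**2. What the Section 4 sentence permits.** The ceiling is 10 split-tattoo subjects. There is no stated floor, and one laser per split is allowed. The wording therefore admits anywhere from 0 to 10 both-laser pairs.

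**3. What a given number of pairs can show.** The documents name no test for this comparison, so these are illustrations.

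The smallest two-sided p from an exact sign or signed-rank test on n untied pairs is 2/2ⁿ. The 95% CI half-width for the mean paired difference is t(0.975, n−1)/√n × SD. The documents give no SD, so the last three columns show grades for assumed SDs of 0.75, 1.0 and 1.5.

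| Pairs | Smallest exact p | Half-width (× SD) | SD 0.75 | SD 1.0 | SD 1.5 |
|---|---|---|---|---|---|
| 3 | 0.25 | 2.48 | 1.86 | 2.48 | 3.73 |
| 5 | 0.0625 | 1.24 | 0.93 | 1.24 | 1.86 |
| 6 | 0.031 | 1.05 | 0.79 | 1.05 | 1.57 |
| 10 | 0.002 | 0.72 | 0.54 | 0.72 | 1.07 |

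Six pairs reach 0.05 only if all six favour the same laser. One tie leaves five pairs and p = 0.0625 at best. One reversal gives at least 4/64 = 0.0625 (signed-rank) or 14/64 = 0.219 (sign test). A paired t-test can reach 0.05 with fewer pairs, but only by assuming normal differences on a four-level grade.

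**4. Power on the SAP's scale.** Assume a paired-difference SD of 1.07, the largest for which a paired t-test needs 6. Power for a 2-point between-laser difference is 43% with 3 pairs, 87% with 5, 95% with 6 and over 99% with 10. For a 1-point difference it is 46% with 6 pairs and 75% with 10. With 10 pairs and a 1-point difference, power runs from 96% (SD 0.75) to 47% (SD 1.5).

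**5. Allocation of parts.** Reading Sections 4, 5, 5.1, 5.3.2, 5.3.3 and 5.4 together, none says which part of a tattoo gets which laser, who decides, or when. The choice is left open to the operator.

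**The case against.** The strongest reply is that the split-tattoo subjects are one of the SAP's ten subgroups. The ceiling of 10 in Section 4 matches the SAP's ceiling per group, the SAP calls the groups treatment subgroups, and it leaves their basis partly open. On that reading 6 is the required number and 10 the enrolment ceiling. This is plausible and may be what the sponsor intends. But no text says so, and it would not cure 'and/or': six split tattoos would still not have to be six PicoSure–RevLite pairs. Nor would it settle how the parts are assigned.

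A second reply is that the sponsor plainly means both lasers, since the comparison is a stated objective and Section 4 says subjects will receive split treatments. That makes zero pairs an extreme reading. It stands as a reason not to predict failure. It is no reason to keep wording that permits a shortfall.

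Third, no between-laser hypothesis or test is stated, so a significance threshold borrowed from the subgroup calculation may not apply. That also stands. The p-values above only illustrate what few pairs can show. The interval widths need no hypothesis test, though they rest on a t interval.

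**Conclusion.** The point holds and should be fixed. A primary objective depends on one sentence that neither requires both lasers on a split tattoo nor sets a minimum, and no section assigns tattoo parts to lasers. Two consequences follow. There may be fewer both-laser pairs than the comparison needs, which is possible but not certain. And the parts may be chosen by the operator, which can bias the comparison at any number of pairs.

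On size, moving from 10 pairs to 6 widens the 95% CI half-width from 0.72 to 1.05 SD, and 3 pairs take it to 2.48 SD. Turning these into grades requires an assumed SD. If 6 to 10 true pairs complete, the lasers differ by 2 points and the SD is about 1.07 or less, power would be adequate.

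A reader might infer that the trial will have no usable data on the comparison. The documents do not support that. The sentence allows up to 10 pairs, the objective points towards using both lasers, and even a RevLite-only subject would permit a weaker, unpaired comparison with PicoSure subjects. A reader might also infer that the SAP's 6 is the sample size for the comparison, or that it certainly is not. The text settles neither.

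**What to change.** - **Protocol Section 4:** replace 'and/or' so that each comparison subject receives both lasers on separate parts of the same tattoo, with parts assigned to lasers at random before the first treatment. Count single-laser splits separately.
- **SAP, PicoRev Sample Size Rationale:** say whether the split-tattoo subjects are one of the ten subgroups. Then either tie the comparison to a stated minimum number of both-laser subjects within the existing cap of 10 (for example, the SAP's own 6 evaluable), or list it as exploratory and give the expected CI width. If 6 is chosen, state the between-laser difference and SD it assumes, because six pairs leave no room for a tie or reversal in an exact test.
- **Protocol Section 15:** analyse these subjects as a within-subject PicoSure-minus-RevLite difference in blinded clearance score, reported with a 95% CI and the number of pairs.

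The cost is a short formal amendment with written IRB approval, as Protocol Section 19 requires, and a simple randomisation list for tattoo parts. It needs no extra subjects or visits.

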4.1 Inclusion Criteria

1. Is a healthy male or female between 18 and 65 years old.
2. Is willing to consent to participate in the study.
3. Is willing to comply with all requirements of the study including being photographed, following post treatment care and attending all treatment and follow up visits.

4.2 Exclusion Criteria:

1. The subject is female and pregnant, has been pregnant within the last 3 months, is currently breast feeding or planning a pregnancy during the study period.
2. The subject is hypersensitive to light exposure OR takes photo sensitizing medication.
3. The subject has active or localized systemic infections.

4. The subject has a coagulation disorder or is currently using anti-coagulation medication (including but not limited to heavy aspirin therapy {greater than 81 mg per day}).
5. The subject has any condition which, in the investigator's opinion, would make it unsafe for the subject to participate in this research study.
6. The subject is currently enrolled in an investigational drug or device trial, or has received an investigational drug or been treated with an investigational device within 3 months prior to entering this study.
7. The subject has used Accutane within 6 months prior to enrollment.
8. The subject has the need to be exposed to artificial tanning devices or excessive sunlight during the trial.
9. The subject has had prior treatment with parenteral gold therapy (gold sodium thiomalate).
10. The subject has a history of keloid scar formation.
11. The subject has evidence of compromised wound healing.
12. The subject has a history of basal cell carcinoma, squamous cell carcinoma or melanoma.
13. The subject has a history of immunosuppression/immune deficiency disorders (including HIV infection or AIDS) or use of immunosuppressive medications or has an autoimmune disorder.
14. The subject has red tattoo ink allergy

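### No eligibility criterion covers earlier removal treatment of the study tattoo, so fading from a recent session with a cleared laser may be counted as study-laser clearance

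*Protocol*

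**What the plan says.** Protocol section 4.2, criterion 6, excludes anyone now in an investigational drug or device trial, and anyone who has received an investigational drug "or been treated with an investigational device within 3 months prior to entering this study". The other limits on earlier treatment concern drugs: criterion 7 ("The subject has used Accutane within 6 months prior to enrollment") and criterion 9 (parenteral gold at any time). Criterion 5 gives the investigator discretion, but only over conditions that "would make it unsafe for the subject to participate in this research study".

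The lasers in ordinary use for this purpose are not investigational. Section 2 says that Q-switched Alexandrite and Nd:YAG "lasers emitting wavelengths of 1064nm, 755nm and 532nm, are routinely used in the removal of unwanted tattoos". Section 3 adds: "The RevLite Q-Switched Nd:YAG is cleared under FDA K083899 for Tattoo Removal", and "The PICOSURE laser has been cleared by the FDA under 510 (k) K121346 for the removal of tattoos and benign pigmented lesions".

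Section 5.7.1 defines the efficacy assessment: "Blinded evaluators will grade the tattoo clearance of photographs taken of the subjects at baseline and post treatment". Section 15 (Data Analysis) and the SAP describe no adjustment or stratification for earlier laser treatment. The SAP speaks only of subgroups formed on demographics, tattoo characteristics and further parameters still to be identified.

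**The concern.** A before-after endpoint needs a baseline that would stay put without the study treatment. Section 2 describes removal in two stages: the pulse breaks up the pigment, and scavenger cells then carry it away. Sessions are spaced at about 6 weeks in the Background and 4 to 12 weeks in section 5.3.2. A baseline photograph taken soon after an outside session may therefore show a tattoo that is still fading.

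The plan places its follow-up visit at 2 months, plus or minus 1 month, but requires no wait between an outside session and the baseline photograph.

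Two results are exposed. One is absolute clearance, which underlies the objective of establishing treatment parameters. The other is any comparison between treatment subgroups: if recently treated tattoos fall unevenly across small subgroups, the difference can look like an effect of laser settings.

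**Working it through.** **Step 1: is the gap closed elsewhere?** Take a tattoo treated with a cleared laser a few weeks before baseline and apply each relevant criterion.

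- Criterion 6 does not apply, because the device was not investigational.
- Criteria 7 and 9 do not apply, because they concern drugs.
- Criterion 5 does not apply unless the earlier session makes participation unsafe. A confounded baseline is not a safety matter.
- The three inclusion criteria in section 4.1 do not mention treatment history.
- Medical history is reviewed (sections 5.1, 5.2 and 5.4). Sections 5.1 and 5.2 tie that review to verifying the criteria, none of which asks about tattoo removal.

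The tattoo is eligible.

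**Step 2: the plan's own sample size.** The SAP gives 6 per subgroup for an effect of 2 on a 0-3 scale, with 95% power and two-sided 0.05. It states neither a standard deviation nor a test, so 6 cannot be reproduced from stated inputs alone. With an assumed standard deviation of 1, a one-sample t-test needs 5.54, rounded up to 6, which matches. Raising 6 to 10 allows for 1 - 6/10 = 40% loss, and 10 groups of 10 give the 100 subjects. A washout leaves this calculation unchanged; 6 matters here only as the denominator of a subgroup mean.

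**Step 3: illustration of the shift.** Let f be the share of a subgroup recently treated elsewhere and c the carry-over in grades falling after baseline. The subgroup mean is inflated by f × c. Both inputs are assumptions; the documents give neither.

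- One affected subject in 6, c = 1: 1/6 × 1 = 0.17 grade; 0.17/2 = about 8% of the planned effect.
- Two affected in 6, c = 1: 2/6 × 1 = 0.33 grade, about 17%.
- One affected in 10, c = 1: 1/10 × 1 = 0.10 grade, 5%.
- Range f = 0.10 to 0.50 and c = 0.25 to 1.0: from 0.10 × 0.25 = 0.025 grade (1.25% of 2) to 0.50 × 1.0 = 0.50 grade (25% of 2).

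**Step 4: where it cancels.** Section 4 allows up to 10 split-tattoo subjects. If both halves had the same earlier treatment, each half carries the same c, so the expected difference between halves is shifted by c - c = 0. Each half's absolute clearance is still inflated. For the other subjects, up to 100 - 10 = 90 if both limits are reached, no within-subject control is described.

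**The case against.** The strongest reply is that the text shows a gap but not a bias. Section 2 says that clearing follows the pulse but not for how long, and a usual session interval is not a measured fading time. Nor do the documents say how many candidates will have been treated before. This stands: the point is a risk of unknown size.

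Several stronger readings are tempting and are not supported.

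- *A large misattributed effect.* From the 2-4 treatments in section 2, a reader might infer that one earlier session is worth 25% (1/4) to 50% (1/2) of total clearance. Assuming that 25-100% of its fading falls after baseline gives 0.25 × 25% = 6 up to 1.0 × 50% = 50 percentage points, against the 50% that the SAP treats as an effect. That range is per affected subject, assumes equal fading per session, and ignores the rest of the section. At ten treatments the same method gives 2.5-10 points, and at twenty 1.25-5. A tattoo that clears in two sessions might also clear fully within the up to 10 study treatments, so carry-over could change the number of sessions more than the final grade.
- *The effect could never be removed afterwards.* Medical history is a scheduled screening item, and the case report form (Appendix B) was not available to this review. It may already capture earlier sessions.
- *Old scarring or pigment change would be counted as study events.* The visit schedule in section 5.4 has photographs and an events assessment at screening/baseline. Section 7 records adverse events from the first treatment and rates their relationship, with categories that allow for other therapeutic interventions. Late-emerging changes could still be misattributed, but this is not a main ground for the point.
- *Three months is the correct interval.* The documents give no carry-over duration from which to derive one.

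**Conclusion.** The point holds as a gap in eligibility with a possible, unquantified effect on the clearance endpoint. Applied as written, the criteria admit a tattoo lasered with a cleared device shortly before baseline, and the planned comparison has no stated means of separating its residual fading from clearance by the study laser. Absolute clearance and between-subgroup comparisons are affected. The device difference within split tattoos is largely protected, provided that both halves share the same treatment history.

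The 0.17 grade (about 8% of the planned effect) for one affected subject in 6 rests on an assumed carry-over of 1 grade. It shows how sensitive a small subgroup mean is and does not estimate the bias in this trial. A reader might infer that carry-over is certain to be credited to the study laser; the documents support only that it may be. The change is worth making because it is cheap and the subgroups are small.

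**What to change.** - In section 4.2, extend the criterion 6 washout to any removal treatment of the study tattoo, by a cleared or an investigational device, before the baseline photograph. The existing 3-month window is a convenient default; the sponsor may justify another interval.
- At screening, record the number of earlier removal sessions on the study tattoo and the date of the last one, if the case report form does not already do so.
- In section 15 and the SAP, state that clearance will be reported by prior-treatment status. This also covers subjects with a long treatment history outside the window, for whom a washout alone does nothing.

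The cost is one amended criterion, at most two data fields and one additional breakdown in the report. The downside is that some recently treated candidates must wait or are excluded; the documents give no basis for saying how many.
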